8.6 Four-month Booster Session

Among the intervention group, the study will attempt to schedule the participant for a brief 15-minute check-in by phone or web-video 4-months (± 1 month) after the initial counseling session. For intervention subjects who have such booster sessions outside the 3-5 month window, their data will be flagged but would still remain eligible for analysis. The following outcomes will be captured at this time point:

- Study clinician rating of participants' action plan completion, ranging from 0 (none of the plan completed and no apparent intention to complete the plan) to 10 (action plan complete; see **Appendix**).
- Similar to the baseline session, we will cease trying to schedule this booster session if no session has been scheduled by 5 months after the initial counseling session. We will still attempt to reassess their health status at the 1-year time point with a 2nd questionnaire and home visit. *If a participant has to cancel and reschedule, the rescheduled date can fall outside the 5 month deadline.*

Among the control group, participants will receive a generic thank you letter by mail for participating. No outcomes will be measured in this group at this time point.

8.7 Second Questionnaire and Home Visit

The 2nd questionnaire and home visit should take place approximately 1-year after the initial questionnaire and home visit. The study will send participants an abridged version of the baseline questionnaire (by mail, with phone/email follow-up as necessary) with a reminder that a 2nd home visit is also due soon. After the participants complete the follow-up questionnaire, the study will work with the exam service provider to contact the participant to arrange for the 2nd home visit. The study will attempt to have all 2nd home visits occur within 3 months of the 1-year anniversary, and visits that occur outside that 3-month window will be flagged (but remain eligible for analysis). The following outcomes will be measured at this time point:

- Same physical measurements as before: standing height, weight, blood pressure at rest (3 times), and waist circumference.
- Blood draw (no fasting required): lipid profile, blood glucose, hemoglobin A1c, and insulin (**Table 5**; other assays will not be drawn unless they could not be drawn at the first home visit).
- If the exam service provider is unsuccessful in obtaining blood due to a technical issue, or the participant refuses the venous blood draw at the second visit, we will offer the participant the option of a finger poke to obtain a blood spot sample (i.e., dried blood spot, DBS). Blood spots will only be offered as a back-up option at the second visit.
- Handling of any critical results will be conducted similarly as per the baseline home visit (see **Section 8.5** above). In contrast to venous samples, DBS-based measurements of the lipid profile, glucose, insulin, and hemoglobin A1c will not be released back to participants or their providers. This is because such measurements are not performed in a CLIA-certified setting and are currently designed for epidemiologic research only (and not for clinical care), and also will be batched (in contrast to venous samples which are processed in near real-time).

Should home visits be completely declined or impossible to conduct (e.g., due to COVID-19 or other public health issues where social distancing is encouraged/mandated), the protocol will permit

substitution of a completely remote assessment procedure for the follow-up visit. This would necessarily be slightly modified from the exam service provider-obtained home visit in the following ways:

- Physical measurements will only include: weight and blood pressure at rest (3 times). These will be collected using a scale and blood pressure cuff that the study can provide to study participants. If participants already have a digital scale at home, they can use their own scale in place of a scale the study provides. Blood pressure cuff and scale can be kept by participants and do not need to be returned to the study team. These results can be returned to participant and their primary healthcare provider, but would be clearly noted as participant-collected.
- Blood draw will be replaced by the DBS method specified above, with the same caveat that DBS results cannot be returned to participants.

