5.0 SUBJECT ELIGIBILITY

5.1 Inclusion Criteria

For Primary Aim 1:

- 5.1.1 CCSS participant who is age ≥ 18 years at time of initial consent.
- 5.1.2 High CV risk status based on CCSS risk prediction models for cardiomyopathy and ischemic heart disease.
- 5.1.3 Living in the U.S., within 50 miles of a designated exam service provider (e.g., EMSI) based on CCSS's available contact information at the time of approach.
- 5.1.4 Able to read, write, and speak English.
- 5.1.5 Ability to understand and the willingness to provide informed consent.

For Primary Aim 2, in addition to the satisfying the above criteria, participants must also meet the following criteria:

5.1.6 Abnormal CV condition identified on home visit. Defined as having at least one of the following:

- Average blood pressure $\geq 130/80$ mmHg ($\geq 130/80$ if existing hypertension diagnosis)
- LDL ≥ 160 mg/dL
- Triglyceride ≥ 150 mg/dL (if ≥ 10 hours fast) or ≥ 200 mg/dL (if < 10 hours fast)
- If not known to be diabetic: Glucose ≥ 100 mg/dL (if ≥ 8 hours fast) or ≥ 140 mg/dL (if < 8 hours fast)
- HbA1c $\geq 5.7\%$ (if not known to be diabetic), HbA1c $\geq 7\%$ (if known diabetic).

5.1.7 Be free of any known (self-reported) ischemic heart disease or cardiomyopathy.

5.1.8 Have access to a telephone or computer to receive a phone or web video counseling/intervention session at baseline and at 4 months.

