8.2 First Home Visit

This will include:

- Signature on HIPAA authorization and Medical Record Release form (optional).
- Standing height: in centimeters, to the nearest 0.1 cm.
- Weight: in kilograms, to the nearest 0.1 kg.
- Blood pressure at rest: 3 times; each at least 3 minutes apart.
- Waist circumference: in centimeters, to the nearest 0.1 cm; just above the uppermost lateral border of the right ilium [hip bone]; at the end of a normal expiration.
- Blood draw (no fasting required): lipid profile, blood glucose, hemoglobin A1c, insulin, and samples for ancillary biological studies (**Table 5**).

TABLE 5. Overview of blood samples, draw order, vial type, volume.

Draw order / Analyte	Vial type	Volume
1) Lipid profile, glucose, insulin level*	Heparin plasma separator tube (green top)	3.0 mL
2) Hemoglobin A1c*	EDTA tube (lavender top)	1.0 mL
3) Protein & DNA-based assays	EDTA tube (lavender top)	7.5 mL
4) General chemistries	Serum separator tube (red/gray top)	7.5 mL
5) Proteomics, metabolomics	EDTA separator tube (pearl)	7.5 mL
6) RNA for gene expression	PAXgene tube	2.5 mL

*These also will be drawn at the 2nd home visit; remaining tubes would NOT be drawn at the 2nd home visit unless they could not be successfully drawn at the first visit. 2nd home visit only: blood spot offered for failed venous draws.

With our 7/2020 protocol modification, in response to the unexpected closure of the study's original exam service provider (EMSI), replacement service providers may include those that do not provide home-based services but rather fixed laboratory / service centers that the participant travels to in order to obtain the specified research blood draw. In these instances, only tubes 1-2 (**Table 5**) will be drawn and processed on-site (i.e., tubes 3-6 will not be drawn).

Rarely, in past experiences with our pilot data and similar CCSS home visit-based studies, exam service staff will be unsuccessful in obtaining blood given technical issues. In this situation, the participant will be offered the choice of having the procedure be rescheduled to another date. *If the participant refuses and the primary study endpoints (lipid profile, blood glucose, and hemoglobin A1c) cannot be collected, then the patient will not be eligible to continue on the study.* Any partial results will still be sent back to the participant and their designated primary care provider.

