13.2 Aim 2 Analytic Plan

Hypothesis: survivors randomized to the intervention will have a lower probability of having an undertreated CV risk factor compared with the control group at 1-year follow-up.

Primary analyses: We will describe baseline characteristics (including mean/median values of our target CV parameters) and proportions of underdiagnosis and undertreatment of our 3 CV risk factors. Our primary analysis will focus on the difference in the probability of having a CV risk factor undertreated after the 2nd home visit across the 2 study arms. As in Aim 1, undertreatment of hypertension, dyslipidemia, and diabetes at the 2nd home visit will be defined as blood pressure $\geq 130/80 \text{ mmHg}$, LDL ≥ 160 or triglyceride $\geq 150 \text{ mg/dL}$ (if fasting <10 hours: $\geq 200 \text{ mg/dL}$), or HbA1c $\geq 7\%$, respectively. Survivors with pre-diabetes at baseline will be undertreated at the 2nd home visit if fasting glucose $\geq 100 \text{ mg/dL}$ (non-fasting $\geq 140 \text{ mg/dL}$) or HbA1c $\geq 5.7\%$. As some survivors may contribute up to 3 outcomes (persistent hypertension, dyslipidemia, and diabetes/pre-diabetes), we will use generalized estimating equations (GEE), accounting for intra-individual correlation of the 3 outcomes, to estimate the overall intervention effect as a single parameter (3-element vector). If multiple survivors share the same primary healthcare provider (unlikely), we will apply random effects models in lieu of GEE given multiple

cluster types. Analyses will be conducted per intent-to-treat, and include all survivors with available end points.

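### Fasting is not matched between visits, so an unchanged triglyceride or pre-diabetes glucose can change primary-outcome status; if the arms fast alike, the main cost is power

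*Combined protocol and SAP*

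**What the plan says.** Section 8.2 describes the first draw as "Blood draw (no fasting required): lipid profile, blood glucose, hemoglobin A1c, insulin, and samples for ancillary biological studies", and section 8.7 describes the second as "Blood draw (no fasting required): lipid profile, blood glucose, hemoglobin A1c, and insulin".

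Entry to the randomised part (5.1.6) uses "Triglyceride ≥ 150 mg/dL (if ≥ 10 hours fast) or ≥ 200 mg/dL (if < 10 hours fast)" and, for those not known to be diabetic, "Glucose ≥ 100 mg/dL (if ≥ 8 hours fast) or ≥ 140 mg/dL (if < 8 hours fast)".

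The primary outcome in 13.2 keeps the same two-level triglyceride limit. For glucose it says: "Survivors with pre-diabetes at baseline will be undertreated at the 2nd home visit if fasting glucose" is at least 100 mg/dL, or at least 140 mg/dL non-fasting, or if HbA1c is at least 5.7%. Section 13.2 gives no hours for glucose; the 8-hour rule comes from 3.3.1, 5.1.6 and Table 6.

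The two levels are intended. Section 3.3.1 explains that fasting draws have become less usual for initial screening in primary care and sets higher limits for non-fasting samples. The limits for blood pressure, LDL and HbA1c do not depend on fasting.

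No section asks participants to repeat their visit-1 fasting state, stratifies or adjusts for it, or plans an analysis by it. The secondary linear models for triglyceride and glucose adjust only for the visit-1 value.

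**The concern.** Section 13.2 scores whether conditions found at visit 1 persist a year later. A limit that moves by 50 or 40 mg/dL with hours since eating brings in a second cause of apparent improvement: the participant ate later before the second draw than before the first. A survivor who enters on a fasting triglyceride of 180 mg/dL and returns at 180 after 9 hours counts as controlled if LDL is below 160. One who enters with pre-diabetes on a fasting glucose of 110 mg/dL and HbA1c 5.5%, and returns unchanged after 7 hours, also counts as controlled.

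The reason given in 3.3.1 concerns initial screening, which suits Aim 1. It does not deal with a repeat measurement that decides a trial endpoint. At stake are the precision of the primary comparison, and its validity if the arms come to fast at different rates. The linear models for triglyceride and glucose also mix fasting and non-fasting values.

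**Working it through.** **1. The steps (5.1.6, 13.2).** Triglyceride: 200 − 150 = 50 mg/dL, at 10 hours. Glucose: 140 − 100 = 40 mg/dL, at 8 hours. A draw between 8 and 10 hours is fasting for glucose and non-fasting for triglyceride.

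**2. Who can switch.**
- Triglyceride 150-199 mg/dL: out of range if fasted, in range if not. Dyslipidemia is LDL or triglyceride, so this decides the outcome only when LDL is below 160.
- Glucose 100-139 mg/dL: the same, but only with pre-diabetes at baseline and HbA1c below 5.7%. Because 3.3.1 classes a fasting glucose of 126 or more as diabetes, the unchanged case for someone who entered on fasting glucose is 100-125. Survivors with diabetes are judged on HbA1c of at least 7% and are untouched.
- The reverse error exists too. A non-fasting triglyceride that enters at 200 or more and falls to 150-199 is controlled if the second draw is non-fasting, but undertreated if the same value is drawn fasted.

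**3. How far a meal offsets the step (assumed values, not in the documents).** Take log-normal fasting triglyceride, median 110-130 mg/dL, log-SD 0.5. The share of fasting-abnormal values that read as controlled when non-fasting is 1 − P(fasting value + rise ≥ 200) / P(fasting value ≥ 150):

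| Rise from meal (mg/dL) | Share reading as controlled |
|---|---|
| 0 | 50-57% |
| 25 | 29-34% |
| 50 | 0% |

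The allowance works when the rise is near 50 and fails for draws just short of 10 hours, where little rise remains.

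**4. The plan's own power (13.2).** Evaluable: 800 × 0.60 × 0.80 = 384, or 192 per arm, stated as about 190. With control risk p₁ = 0.90 and RR 0.88, p₂ = 0.792. Two-sided α = 0.05 is assumed, since 13.2 gives no sidedness. The pooled formula is z = [|p₁ − p₂|√n − 1.96√(2p̄q̄)] / √(p₁q₁ + p₂q₂).
- Numerator: 0.108 × 13.784 − 1.96 × √(2 × 0.846 × 0.154) = 1.489 − 1.001 = 0.488.
- Denominator: √(0.0900 + 0.1647) = 0.505.
- z = 0.967, so power is 83.3%.

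Exact Fisher power is 80.5%. For 50% v 35.5% (RR 0.71) the two figures are 81.8% and 79.5%. The stated 80% is reproduced. This is a person-level calculation, as in the plan; the planned GEE analysis pools up to three outcomes per person.

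**5. Equal misclassification in both arms (rates assumed).** Let a be the share of undertreated outcomes read as controlled and b the reverse. The observed risk is p(1 − a) + (1 − p)b. Power uses the pooled formula at 190 per arm.

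| a / b | 90% v 79.2%: observed | RR | Power | 50% v 35.5%: RR | Power |
|---|---|---|---|---|---|
| 0 / 0 | 0.900 v 0.792 | 0.88 | 83% | 0.71 | 82% |
| 5% / 0 | 0.855 v 0.752 | 0.88 | 71% | 0.71 | 78% |
| 10% / 0 | 0.810 v 0.713 | 0.88 | 60% | 0.71 | 75% |
| 5% / 5% | 0.860 v 0.763 | 0.887 | 68% | 0.739 | 73% |
| 10% / 10% | 0.820 v 0.734 | 0.895 | 53% | 0.768 | 63% |

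One-way loss leaves the RR alone, because (1 − a) cancels, and costs power. The RR moves towards 1 only when b is above zero.

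**6. Unequal fasting by arm (assumed).** If fasting at visit 2 differs by 20 points and 20% of participants have an outcome that turns only on fasting, a null effect shows 0.20 × 0.20 = 4 points. At 90% prevalence that is RR 0.86 / 0.90 = 0.96. The sign depends on which arm fasts more.

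**The case against.** The case for leaving the plan alone is substantial. The two-level limit is a reasoned allowance for non-fasting draws and is used consistently at entry, in the outcome and in reporting results. The primary contrast is between randomised arms at visit 2 under one definition, not change within a person. Both arms get the same draw, and the examiners are blinded. Controls also receive their baseline results with advice to seek follow-up.

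Some switching is ordinary threshold noise. In a simulation with no true change (assumed fasting glucose mean 95-97, between-person SD 9-11, within-person SD 6), 64-73% of those entering at 100-125 mg/dL stayed out of range when fasted again. So 27-36% moved without any change in fasting state.

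Most of this stands, and it rules out three stronger readings that a reader might infer:
- That the mismatch pulls the RR towards 1. One-way loss of equal size does not; the documents give no reverse rate, and 5% each way moves 0.88 only to 0.887.
- That the primary result is biased. Unblinded participants, and clinician review of results in one arm only, make different fasting by arm possible. No section suggests that counselling changes fasting before a visit, and there are no data.
- That two of the three conditions depend generally on meal timing. The step decides the outcome only within the subsets in step 2 of the working.

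What the objection does not answer is that a mismatch can alter an outcome with no change in health, and that asking participants to repeat their fasting state costs almost nothing.

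**Conclusion.** The point holds as a measurement weakness in the primary outcome that is worth correcting. The text alone establishes that fasting is uncontrolled at both visits, that the limits step by 50 and 40 mg/dL, and that nothing in the plan matches or examines fasting state.

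The size is not established. The number of survivors who will switch is unknown, and every meal effect, distribution and misclassification rate above is an assumption. The 5-10% rate applies to all undertreated outcomes, including those on blood pressure that cannot switch, so the rate among fasting-dependent outcomes would have to be higher to reach it. On that assumption, power in the plan's main scenario falls from about 83% to 71-60% with the RR unchanged. The design aims for 80%, so there is little slack. Bias by arm remains a possibility to be checked, not a finding.

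**What to change.** 1. **Section 8.7.** Have the visit-2 appointment notice ask participants in both arms, in the same words, to repeat their visit-1 fasting state. Make it a request, not a condition of the draw. The same line can go with a blood-spot kit when the visit is remote.
2. **Section 13.2.** Report fasting category (10 hours for triglyceride, 8 for glucose) at visits 1 and 2 by arm.
3. **Section 13.2.** Pre-specify a sensitivity analysis of the primary outcome, applied identically to everyone. Restrict it to conditions that qualified at visit 1 on blood pressure, LDL or HbA1c, and score them at visit 2 on those same measures whatever the fasting state. The set is fixed at baseline, so randomisation is preserved. Do not instead count triglyceride and glucose only when fasting state matches. That would condition the endpoint on behaviour after randomisation. It would also still code the glucose example in the concern as controlled, and the triglyceride example whenever LDL is below 160.
4. **Section 13.2.** Add a sensitivity version of the triglyceride and glucose linear models with fasting state at each visit as covariates.

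No cut-point changes. Hours since eating are already needed to apply the limits, so the cost is one line in a notice and some analysis wording. The drawbacks are a slight burden for those who fasted at visit 1, some remaining switches, and fewer outcomes in the sensitivity analysis. If second visits are already under way, items 2 to 4 can still be added before unblinding.

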8.8 Primary healthcare provider measurements

Following the 2nd home visit, accompanying the mailing of a copy of participant materials (intervention group: clinical results and SCP; control group: clinical results only), all designated providers will be asked to answer questions adapted from the NCI/ACS SPARCCS (see **Appendix**).⁶¹

We will also request outpatient clinical records (clinician notes, medication lists, laboratory results) spanning the study period (and up to 2 years prior to the 1st home visit) from all participants' primary healthcare providers. We will abstract records for: 1) documentation of the participant's prior cancer history and CV risk status in relation to past cancer exposures; 2) any reference to a SCP or long-term follow-up guideline; 3) any CV screening planned or undertaken [coded separately]; 4) presence of any of the three target CV risk factors as a diagnosis/problem; and 5) interventions to address any CV risk factor [coding lifestyle or drug prescription separately]. Medications will be reviewed to examine whether, among those undertreated at the 1st home visit, there is subsequent treatment intensification (e.g., going from lifestyle prescription alone to adding medication; from lower to higher drug doses; from single to multiple drugs; **Table 7**), and whether treatment intensity differs across study arms after the intervention.

Medication (class)	Low	Medium	High
Hypertension			
Lisinopril (ACE-inhibitor)	≤10	11-30	>30
Amlodipine (calcium channel blocker)	≤2.5	2.6-9.9	≥10
High cholesterol			
Simvastatin (HMG CoA reductase inhibitor)	<20	20-39	≥40
Diabetes			
Glipizide (sulfonylurea)	<10	10-19	≥20
Insulin			Any dose

Description of how the study will engage with primary healthcare providers is otherwise described in **Section 7.5**.

8.9 Materials returned to participants and primary healthcare providers

Information the study will send (by mail) back to study participants and their designated current primary healthcare provider are summarized in **Table 8**.

TABLE 8. Information the study will mail back to study participants and their current primary healthcare providers.

After the initial home visit / baseline counseling session	After the 4-month booster	After the 2 nd home visit

Intervention group (participant & provider)	Clinical results Survivorship care plan Action Plan	Updated Action Plan	Clinical results Survivorship care plan
Control group (participant & provider)	Clinical results	-	Clinical results Survivorship care plan*

*Mailing of the care plan would not occur until AFTER the control group's designated healthcare providers are surveyed.

8.10 Remote blood pressure monitoring pilot

Following completion of the intervention, we will also approach participants regarding their willingness to perform home blood pressure monitoring (HBPM) via mHealth (i.e., Bluetooth-enabled) devices. The rationale for this is that compared with our standard measurement approach, home monitoring is likely to be more accurate, both in ruling out “white coat” hypertension as well as ruling in “masked” hypertension.⁵⁰ This pilot would seek to enroll 40 participants who have just completed their 2nd home visit (or 1st home visit if all values were normal and they were otherwise not eligible to participate in the randomized controlled trial) and ask them to collect home blood pressures 3 times a week for 4 weeks. A Bluetooth-enabled blood pressure monitor would be provided free of cost to study participants. Participants would be requested to download the blood pressure manufacturer’s mHealth application (app) which will collect measured blood pressure values as well as a 2nd study-specific mHealth app (Eureka, UC San Francisco), which is designed to facilitate mHealth research and transmit research-specific reminders (e.g., phone notifications or texts) and instructions to participants, as well as provide investigators the ability to access the blood pressure values collected on the monitors.

The primary goals of this pilot would be to determine the feasibility of HBPM, including participation rate and the proportion of participants who transmit >75% of requested data (>9 measurements in one month). Secondary goals would be to determine the proportion of individuals who may have “white coat” hypertension (i.e., in-person collected values are systolic ≥130 or diastolic ≥80 mmHg but HBPM average is lower) or “masked” hypertension (i.e., in-person collected values are systolic <130 and diastolic <80 mmHg, but average HBPM is greater). Data from this pilot will be used to inform the feasibility of a future follow-up study that involves using HBPM as part of the study assessment and intervention.

Participants would be approached as part of their final home visit results mailing, and those interested would be instructed to download the Eureka app onto their smartphone and provide informed consent on that app. The study team would follow-up by phone (including text messaging) and/or email among non-responders to determine interest. Participants would be eligible for an additional incentive upon completing this 1-month pilot (choice of either keeping their home blood pressure monitor or a \$50 gift card). As all blood pressure measurements will be visible to participants on both the monitor as well as the manufacturer’s app on their phones, they will be encouraged to share any values with their healthcare provider if they have concerns.

Specific eligibility for this follow-up pilot study would include:

- CHIIP study participant who has completed their 2nd home visit (or 1st home visit if all values were normal and they were otherwise not eligible to participate in the randomized controlled trial);
- Has access to an internet-connected smart phone capable of downloading apps from either Apple or Android-based “app stores”;

- Consents to this follow-up study, which includes being willing to download both the blood pressure monitor manufacturer app as well as research Eureka app, and being willing to receive study-specific reminders (phone notifications and/or text reminders);
- Arm circumference is within the parameters of the home blood pressure monitor manufacturer specifications.

